3.3 Secondary Objectives

To assess the toxicity of SABR + Radium-223 in patients with oligometastatic disease.

To determine local control at 12-months after SABR + Radium-223 in patients with oligometastatic disease.

To assess time to locoregional progression, time to distant progression, time to new metastasis and duration of response after randomization to SABR *versus* SABR + Radium-223.

To assess ADT-free survival after randomization to SABR *versus* SABR + Radium-223.

To assess quality of life following completion of SABR + Radium-223.

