6.7.2 Imaging

Bone scan and CT/MRI of metastatic site(s) will be at 6- and 12-months for all patients, unless indicated more frequently by clinical or laboratory findings.

If applicable, bone scan and ¹⁸F-DCFPyL (“PyL”) -PET/CT of metastatic site(s) will be at 6 months for all patients, unless indicated more frequently by clinical or laboratory findings. The results of the ¹⁸F-DCFPyL (“PyL”) -PET/CT will be made available to the treating physicians prior to enrollment to determine treatment.

The CT portion of the ¹⁸F-DCFPyL (“PyL”) -PET/CT scans at 6 months will be used to determine radiographic response based on RECIST 1.1 criteria for soft tissue lesions. Similarly, the CT or MRI scans at 6- and 12-months will be used to determine radiographic response based on RECIST 1.1 criteria for soft tissue lesions.

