9. MEASUREMENT OF EFFECT

9.1 Antitumor Effect – Metastatic Tumors

For the purposes of this study, patients should be re-evaluated for radiographic response 6- and 12-months after randomization. Trial radiologists evaluating for treatment responses will be blinded to the treatment group and treatment specifics (lesions treated with SABR).

Response and progression will be evaluated in three ways:

- 1) Using Response Evaluation Criteria in Solid Tumors (RECIST 1.1) Committee definition. Changes in only the largest diameter (uni-dimensional measurement) of the tumor lesions are used in the RECIST criteria.
- 2) Lesions by bone scan will be evaluated as positive, negative or no change. MRI of the bone lesion can be used to clarify equivocal lesions.
- 3) Serial PSA changes.

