14.1.2 Secondary Objectives

- To describe the toxicity of SABR and SABR + Radium-223 delivered for the population enrolled using grading with CTCAE v. 4.0
- To determine local control at 12-months after SABR and SABR + Radium-223 in patients with oligometastatic disease.

- To assess time to locoregional progression, time to distant progression, time to new metastasis and duration of response after randomization to SABR *versus* SABR + Radium-223.
- To assess ADT-free survival (ADT-FS) of this patient population after randomization defined as the time interval between the day of randomization and the initiation of ADT. ADT will typically be initiated on progression and/or development of new metastases.
- To assess quality of life following SABR *versus* SABR + Radium-223 arms. Brief Pain Inventory form which will be filled out by the patient at the treatment response intervals outlined above.

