14.5 Analysis of Secondary Objectives

- For safety analysis, adverse events will be summarized by type and grade.
- Kaplan-Meier (KM) estimates will be used to summarize ADT-free survival (ADT-FS), time to locoregional progression (TTLP), time to distant progression (TTDP), time to new metastasis (TNM) and duration of response over time. The median PFS, ADT-FS, TTLP, TTDP TNM and duration of response will be reported.
- The efficacy of SABR + Radium-223 in men with oligometastatic disease will also be determined by measuring local control of each lesion at 12-months.

Each metastatic lesion will be considered a target lesion and independently evaluated for response using RECIST 1.1 or bone scan evaluation criteria above. The lesion will be coded as being locally controlled if it is considered stable radiographic disease or if there is evidence of a partial or complete response. Local control assessment will start at three months following randomization and continuous assessment will be pursued during the follow-up period. The proportion of the lesions that have a stable or better response will be estimated using generalized estimating equation.

- Quality of life will be assessed using the Brief Pain Inventory form. An overall score will be calculated pre-treatment and at the time of the 2nd radiologic reassessment. The change in score will be evaluated with a paired t-test.

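### The comparative quality-of-life objective is analysed only by a paired t-test of within-patient BPI change, which gives no estimate of the difference between arms

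*Combined protocol and SAP*

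**What the plan says.** **Objective.** Section 14.1.2 states: "To assess quality of life following SABR *versus* SABR + Radium-223 arms". The synopsis (section 1) is also worded as one arm versus the other. Section 3.3 is not: "To assess quality of life following completion of SABR + Radium-223".

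**Instrument and timing.** Section 14.1.2 names the "Brief Pain Inventory form which will be filled out by the patient at the treatment response intervals outlined above". Section 9.1 sets those intervals: "patients should be re-evaluated for radiographic response 6- and 12-months after randomization". In section 8, footnote F of both calendars lets the first form be completed on Day 1 or at an SBRT visit. Footnote W (SABR-only calendar) and footnote Z (combination calendar) require the form at months 18 and 24.

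**Analysis.** Section 14.5 states "An overall score will be calculated pre-treatment and at the time of the 2nd radiologic reassessment" and then "The change in score will be evaluated with a paired t-test". It does not define the overall score. Nor does it give the analysis population, the significance level, or whether the test is pooled or run by arm. No other section gives a two-sample test, ANCOVA, mixed model or treatment term for the BPI.

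**Other secondary endpoints in 14.5.** These are summaries: "Kaplan-Meier (KM) estimates will be used to summarize ADT-free survival" and the other time-to-event endpoints, a lesion-level proportion for local control, and adverse events by type and grade. The only between-arm test in section 14 is the log-rank test for PFS (14.4).

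**The concern.** The objective in the statistical section asks how the arms differ, and the named test asks whether patients change over time. Change over time in an uncontrolled comparison mixes treatment effect with disease course and the passage of time. The randomized control arm exists to separate these.

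Followed as written, the plan yields a p-value for change and no prespecified estimate of the randomized difference. Any between-arm statement on quality of life would then rest on a method chosen after the data are seen.

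Three related gaps affect any replacement analysis: the undefined score, a baseline form that may follow treatment, and no statement on forms completed after progression.

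**Working it through.** **1. Plan's own figure.** The documents give no figure for the BPI analysis. The only design calculation is for PFS (14.2), and it reproduces. With exponential medians of 10 and 20 months, accrual A = 18 and follow-up F = 12, the event probability is 1 - (e^(-λF) - e^(-λ(A+F)))/(λA), which gives 0.751 and 0.509. Expected events are 30 × (0.751 + 0.509) = 37.8. One-sided 0.10 power is Φ(√37.8/2 × ln 2 - 1.2816) = 0.802. Drop-out: 60/0.95 = 63.2, rounded up to 64. This calculation does not size the BPI endpoint.

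**2. What the named test estimates.** Let D be a man's follow-up score minus his pre-treatment score.
- Pooled, the paired t-test tests mean(D) = 0 over both arms.
- By arm, it tests mean(D | SABR) = 0 and mean(D | combination) = 0 separately.
- The comparative objective needs mean(D | combination) - mean(D | SABR), or its baseline-adjusted form. Neither version supplies it.

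**3. Illustration.** The documents give no BPI SD, correlation or target difference. Assumed: normal scores with SD 1, two-sided 0.05, pre/post correlation r = 0.5 (range 0.3 to 0.7) and 30 men per arm (from 14.2). The SD of change is √(2(1 - r)) = 1.000 (1.183 to 0.775).

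| Scenario | Quantity | r = 0.3 | r = 0.5 | r = 0.7 |
|---|---|---|---|---|
| Same 0.5 SD change in both arms | Pooled paired test significant | 0.896 | 0.968 | 0.998 |
| | Each within-arm test significant (p) | 0.609 | 0.754 | 0.927 |
| | Exactly one arm significant, 2p(1 - p) | 0.476 | 0.371 | 0.135 |
| Changes of +0.25 and -0.25 SD (chosen so that the pooled change is zero) | Pooled paired test significant (simulated) | 0.045 | 0.044 | 0.039 |
| | Power of ANCOVA for the 0.5 SD arm difference | 0.514 | 0.594 | 0.760 |

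The pooled test is therefore nearly always significant when the arms do not differ, and almost never when they differ in opposite directions.

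**4. Precision of a between-arm estimate.** ANCOVA standard error = √((1/n1 + 1/n2)(1 - r²)), with n1 + n2 - 3 degrees of freedom.
- All month-12 forms present, 30 and 30, r = 0.5: √((2/30) × 0.75) = 0.224. Half-width 2.002 × 0.224 = 0.45 SD (0.49 to 0.37 over the range of r).
- Forms stop at progression: the design medians leave 30 × 2^(-12/10) = 13.1 and 30 × 2^(-12/20) = 19.8 men at month 12. With 13 and 20: √((1/13 + 1/20) × 0.75) = 0.309. Half-width 2.042 × 0.309 = 0.63 SD (0.69 to 0.52).
- A mixed model that adds month-6 forms gives about 0.62 SD in that second case, so it recovers little precision.

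**5. Baseline.** Section 6.8 places the first radium-223 infusion within four weeks of randomization and SABR within 60 days. Under footnote F, a form completed at an SBRT visit can therefore follow radium-223 in the combination arm only. Section 14.5 calls for a pre-treatment score. Adjusting for a score that treatment may have changed in one arm can bias the arm difference.

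**6. After progression.** Progression is a removal criterion (6.11) and a permitted reason for withdrawal (6.15), yet 6.10 and 14.2 follow patients for two years. The plan does not say whether BPI forms continue after progression.

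**7. Visit.** Section 6.7.2 schedules imaging at fixed months "unless indicated more frequently by clinical or laboratory findings". An extra scan can therefore make the second reassessment fall at different times for different men.

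**The case against.** The strongest objection is that the comparative objective is not settled. Section 3.3 names the combination arm only, and a within-arm paired test could fit that wording. The comparative versions say assess rather than compare. This stands as a reason to reconcile the objective before the analysis. It does not rescue the paired test, because section 14.1.2, the statistical statement of the objective, names both arms.

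A second objection is selectivity, since no secondary endpoint in 14.5 has a between-arm test. That is true, and a reader might infer that all of them are wrongly analysed. The documents do not support that: the others are given summaries. Quality of life is the one for which the plan names a hypothesis test, and that test does not match the objective.

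A third objection is that the illustration rests on assumed values, and that the figure for exactly one arm being significant matters only if someone sets two within-arm p-values side by side. The plan does not propose that, so the figure shows why a by-arm version would not serve and does not predict what the investigators will do. Normal scores are also assumed, although men enter with asymptomatic metastases (5.1.1) and scores may cluster near the floor.

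Finally, a mixed model is not required. ANCOVA is enough.

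**Conclusion.** The concern holds as a mismatch between objective and analysis. Where the objective is comparative, the named test does not address it, pooled or by arm. This follows from the text and does not depend on the illustrative numbers.

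Its weight is limited. The endpoint is secondary and unpowered. A reader might infer that the trial's main conclusion is at risk, but PFS has its own log-rank comparison in the intention-to-treat population (14.4) and is unaffected. Nor would the corrected analysis settle the quality-of-life question: a half-width of 0.45 to 0.63 SD at r = 0.5 (0.37 to 0.69 SD over the assumed range) gives an estimate with wide uncertainty. The gain is a prespecified estimate of the randomized difference in place of one chosen afterwards.

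**What to change.** 1. Align section 3.3 with the synopsis and section 14.1.2.
2. Replace the paired t-test sentence in 14.5 with:

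   > BPI pain severity (mean of items 3-6) and pain interference (mean of items 9A-G) at the scheduled month-12 visit will be compared between arms by ANCOVA on arm and baseline score (or a mixed model over scheduled visits), reporting the adjusted difference and 95% CI as estimation; within-arm change is descriptive.

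   Choose one of the two models before analysis. ANCOVA omits men without a month-12 form.
3. Count as baseline only a form completed before the first study treatment, whether SABR or radium-223. Treat a later form as a missing baseline and do not use it as a covariate. State how men with a missing baseline enter the model.
4. Use all available scheduled BPI forms, including those after progression or start of ADT. The sponsor should reconcile 6.11 and 6.15 with 6.10 and 14.2 on whether such forms are collected.

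**Cost.** Wording in 14.5 and one sentence in 3.3, plus the reconciliation in step 4. No new form or visit is needed, because the BPI is already tied to months 6 and 12 and required at months 18 and 24. The drawbacks are limited precision, possible floor effects and some missing baselines.

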14.6 Evaluation of Toxicity

All patients who receive at least one fraction of SABR and Radium-223 will be evaluable for toxicity from the time of their first treatment for SABR and Radium-223.

14.7 Correlative Science

Descriptive statistics will be performed to correlate the temporal CTC, ctDNA, immunophenotyping and immune repertoire metric changes with clinical outcomes.

APPENDIX I: Brief Pain Inventory Form

STUDY ID# _____	HOSPITAL # _____									
DO NOT WRITE ABOVE THIS LINE										
Brief Pain Inventory (Short Form)										
Date: _____ / _____ / _____	Time: _____									
Name: _____	Last	First	Middle Initial							
1. Throughout our lives, most of us have had pain from time to time (such as minor headaches, sprains, and toothaches). Have you had pain other than these everyday kinds of pain today?										
1. Yes		2. No								
2. On the diagram, shade in the areas where you feel pain. Put an X on the area that hurts the most.										
3. Please rate your pain by circling the one number that best describes your pain at its worst in the last 24 hours.										
0 No Pain	1	2	3	4	5	6	7	8	9	10 Pain as bad as you can imagine
4. Please rate your pain by circling the one number that best describes your pain at its least in the last 24 hours.										
0 No Pain	1	2	3	4	5	6	7	8	9	10 Pain as bad as you can imagine
5. Please rate your pain by circling the one number that best describes your pain on the average.										
0 No Pain	1	2	3	4	5	6	7	8	9	10 Pain as bad as you can imagine
6. Please rate your pain by circling the one number that tells how much pain you have right now.										
0 No Pain	1	2	3	4	5	6	7	8	9	10 Pain as bad as you can imagine

7. What treatments or medications are you receiving for your pain?

8. In the last 24 hours, how much relief have pain treatments or medications provided? Please circle the one percentage that most shows how much relief you have received.

0% 10% 20% 30% 40% 50% 60% 70% 80% 90% 100%
No Relief Complete Relief

9. Circle the one number that describes how, during the past 24 hours, pain has interfered with your:

A. General Activity

0 1 2 3 4 5 6 7 8 9 10
Does not Interfere Completely Interferes

B. Mood

0 1 2 3 4 5 6 7 8 9 10
Does not Interfere Completely Interferes

C. Walking Ability

0 1 2 3 4 5 6 7 8 9 10
Does not Interfere Completely Interferes

D. Normal Work (includes both work outside the home and housework)

0 1 2 3 4 5 6 7 8 9 10
Does not Interfere Completely Interferes

E. Relations with other people

0 1 2 3 4 5 6 7 8 9 10
Does not Interfere Completely Interferes

F. Sleep

0 1 2 3 4 5 6 7 8 9 10
Does not Interfere Completely Interferes

G. Enjoyment of life

0 1 2 3 4 5 6 7 8 9 10
Does not Interfere Completely Interferes

Copyright 1991 [name]
Pain Research Group
All rights reserved.
Used by permission.

APPENDIX II: Performance Status Criteria

ECOG Performance Status Scale		Karnofsky Performance Scale	
Grade	Descriptions	Percent	Description
0	Normal activity. Fully active, able to carry on all pre-disease performance without restriction.	100	Normal, no complaints, no evidence of disease.
		90	Able to carry on normal activity; minor signs or symptoms of disease.
1	Symptoms, but ambulatory. Restricted in physically strenuous activity, but ambulatory and able to carry out work of a light or sedentary nature (e.g., light housework, office work).	80	Normal activity with effort; some signs or symptoms of disease.
		70	Cares for self, unable to carry on normal activity or to do active work.
2	In bed <50% of the time. Ambulatory and capable of all self-care, but unable to carry out any work activities. Up and about more than 50% of waking hours.	60	Requires occasional assistance, but is able to care for most of his/her needs.
		50	Requires considerable assistance and frequent medical care.
3	In bed >50% of the time. Capable of only limited self-care, confined to bed or chair more than 50% of waking hours.	40	Disabled, requires special care and assistance.
		30	Severely disabled, hospitalization indicated. Death not imminent.
4	100% bedridden. Completely disabled. Cannot carry on any self-care. Totally confined to bed or chair.	20	Very sick, hospitalization indicated. Death not imminent.
		10	Moribund, fatal processes progressing rapidly.
5	Dead.	0	Dead.

APPENDIX III: CAPP-Seq Sample Collection & Processing

[name] Lab Blood Processing Protocol (version 122314)

❖ **Materials** (check to make sure you have all of it before you start)

- Filtered P2000 pipette tips
- P-2000 pipette
- 2.0-mL Eppendorf tubes
- Patient's blood - usually 30 mL in 3 "purple top" tubes (EDTA) per time point.
Blood should be kept on ice or in refrigerator after drawing and processed as soon as possible to minimize lysis of WBCs and release of cellular genomic DNA into plasma

❖ **Methods**

1. Spin samples in the clinical centrifuge using the settings: 3,500rpm, 10min, 4C
2. While you wait, label tubes
3. After spinning, carefully remove lavender top tubes from centrifuge. Do not disturb the separated plasma and cell-free whole blood
 - i. Tip: It helps to put all the tubes into one holder and carefully carry the holder to the hood
4. Using a filtered tip and p-2000 pipet aliquot ~1.8 mL clear plasma (not all the way to the top since tops of tubes tend to pop open upon freezing if filled all the way) into a 2.0 mL Eppendorf tube. Repeat until you have aliquoted the plasma from all the purple-top tubes into 2.0 mL Eppendorf tubes. With the tubes that have only the buffy coat and RBC remaining, mix the buffy coat and cell-free whole blood using a pipette tip and aliquot ~1.8 mL into a 2.0 mL Eppendorf tube. Repeat so you have a second 2.0 mL Eppendorf tube containing the buffy coat and RBC mixed together.
5. Put Eppendorf tubes into -80C freezer.
6. Write down **# of plasma tubes stored, box number, date of blood draw, time of storage** on the top of patients' requisition forms.
7. Enter the blood draw information into REDCap database.

APPENDIX IV: EPIC-HD CTC Sample Collection & Processing

EPIC SCIENCES, INC.
[name]
[name]

CTC Sample Collection in Streck Cell-Free DNA BCT Tubes

IMPORTANT: The first 5 mL of blood collected from the fresh venipuncture **cannot** be used for the collection into the Streck tubes due to possibility of contaminating epithelial cells during venipuncture. Please ensure that at least one blood tube of 5 mL or more is collected prior to collection of the CTC sample to avoid adversely affecting the test results.

Prevention of Backflow:

Since Streck Cell-Free DNA BCT tubes contain chemical additives, it is important to avoid possible backflow from the tube. To guard against backflow, observe the following precautions:

- Keep patient's arm in the downward position during the collection procedure.
- Hold the tube with the stopper uppermost.
- Release tourniquet once the blood starts to flow into the tube, or within 2 minutes of application.
- Tube contents should not touch stopper or the end of the needle during the collection procedure.

Blood Collection Instructions:

**Schedule courier for same-day sample pic-up prior to collection

1. Confirm blood tube is not expired. Expired tubes should not be used for blood collection.
2. Draw whole blood sample into 10 mL Streck Cell-Free DNA BCT tube (*see note regarding prevention of backflow). Fill tube until blood flow stops. NOTE: Epic requires a minimum of 4mL blood per sample, but a full 10 mL tube of blood should be provided when possible.
3. Remove tube from adapter and immediately mix by gentle inversion 8 to 10 times. Tube inversion prevents clotting. Inadequate or delayed mixing may result in inaccurate test results.
4. Label the tube with subject's identification and date and time of blood draw.
5. Keep sample at room temperature and ship on day of collection.

Sample Shipment Instructions:

Samples are processed the same day as receipt. Priority is given to the samples that had notification the day prior. Epic is able to process samples up to 96 hours after the initial blood draw, but it is preferable to process the blood before the 48 hour mark for optimal CTC retention and data integrity purposes.

EPIC SCIENCES, INC.
[name]
[name]

The total number of slides created is dependent upon the patient's WBC count and amount of blood provided. Each tube should be labeled with the Study and Subject ID. Each sample sent should be accompanied by a requisition form, filled out by the site, listing the study ID, subject ID, draw date, draw time, and time point (if applicable). To avoid weekend delays, mark Saturday delivery if shipping on Friday.

Samples should be sent overnight in ambient shippers on the day the blood sample is drawn.

Epic Sciences receives samples Monday through Saturday from 8:00 a.m. to 5:00 p.m., excluding U.S. holidays. Incoming sample notifications should be sent during normal business hours on the day of shipment by email to [contact] or by fax at [[contact]]([contact]). For samples that will be processed at LabCorp Belgium, please send the sample notification email to [contact]. For samples that will be processed at LabCorp Singapore, please send the sample notification email to [contact].

This email/fax should include:

- 1) Study ID
- 2) Subject ID (and timepoint if applicable)
- 3) Tracking Number
- 4) Number of samples being shipped
- 5) Date and time of each blood sample draw

APPENDIX V: ImmunoSEQ Sample Collection & Processing

Human Sample Preparation Guidelines

TCR IMMUNOSEQ ASSAY SAMPLE GUIDELINES					
Sample type	Resolution				Max Depth
	Survey	Deep	Ultra Deep	Max Depth	
Sorted T cells	60,000 cells ^a 1 µg DNA 50 µL vol.	200,000 cells 3 µg DNA 125 µL vol.	800,000 cells 12 µg DNA 400 µL vol.	4,000,000 cells 48 µg DNA 700 µL vol.	
PBMCs	120,000 cells 2 µg DNA 50 µL vol.	400,000 cells 6 µg DNA 125 µL vol.	1,600,000 cells 24 µg DNA 400 µL vol.	8,000,000 cells 96 µg DNA 700 µL vol.	
Whole blood	2 mL blood 4 µg DNA	4 mL blood 12 µg DNA	10 mL blood 48 µg DNA		Contact Technical Support
Lymphoid tissue ^b	25 microns FFPE 10 mg FF tissue 1 µg DNA		3 µg DNA		Contact Technical Support
Non-lymphoid tissue	25 microns FFPE 10 mg FF tissue 3 µg DNA		9 µg DNA		Not recommended

^a1000 cells is the absolute minimum number of cells accepted.
^bDeep resolution is recommended for lymphoid tissue samples.

NOTE: In order to sequence only rearranged TCRG receptors originating from gamma/delta T cells in PBMCs and tissue samples, a cell sort must be performed prior to receipt of samples by Adaptive Biotechnologies. Unsorted cells will result in the amplification of rearranged TCRG receptors from both gamma/delta and alpha/beta T cells.

cDNA GUIDELINES

- A minimum of 150 ng of RNA is recommended as starting material for the reverse transcription step
- Adaptive targets 10-fold sequencing coverage of each TCR or BCR template
- Using cDNA as an input source will limit available applications

BCR IMMUNOSEQ ASSAY SAMPLE GUIDELINES

Sample type	Resolution			
	Survey	Deep	Ultra Deep	Max Depth
Sorted B cells	60,000 cells ^a 1 µg DNA 50 µL vol.	200,000 cells 3 µg DNA 125 µL vol.	800,000 cells 12 µg DNA 400 µL vol.	4,000,000 cells 48 µg DNA 700 µL vol.
PBMCs/bone marrow ^b	600,000 cells 4 µg DNA 50 µL vol.	2,000,000 cells 12 µg DNA 125 µL vol.		Contact Technical Support
Lymphoid tissue	10 mg FF tissue 1 µg DNA	3 µg DNA		
Non-lymphoid tissue	10 mg FF tissue 3 µg DNA	9 µg DNA		Not recommended

^a1000 cells is the absolute minimum number of cells accepted.

^bB cells represent a small fraction of the total PBMC population; this resolution may not be appropriate for all projects.

DESCRIPTION OF PROFILING RESOLUTIONS: SURVEY VS. DEEP

Resolution	Considerations for choosing resolution
Survey	
 • Clonal samples • Samples with low numbers of T or B cells (<100,000 estimated T or B cells cells) • Samples derived from most non-lymphoid tissues
Deep	
 • Studying the peripheral immune repertoire (e.g. whole blood, peripheral blood mononuclear cells [PBMCs], or lymphoid tissue) • Samples requiring greater sensitivity (detection of rare clones) • Experiments assessing a broader range of the repertoire

RECOMMENDATIONS FOR SAMPLE PREPARATION

Isolating DNA from different sample types

Sorted cells

- Sorting fixed cells into HEPES buffer (PBS with 2% FBS and 0.025M HEPES) can boost the DNA yield from the cell pellets
- When preparing fixed cells for fluorescence-activated cell sorting (FACS), a concentration of 0.5%–2.0% PFA is recommended. Higher concentrations of PFA can fragment the DNA, which will result in reduced PCR amplification efficiency
- Cells should arrive in no more than 200 μ L of buffer

Tissue

- A tissue homogenizer with homogenization buffer is recommended for disruption of fresh or frozen tissue samples
- Example kit for DNA extraction:
 - Qiagen DNeasy™ Blood & Tissue Kit (Mini Spin Columns)
 - Qiagen QIAamp™ DNA FFPE Tissue Kit

Blood, PBMCs, or bone marrow

- ACD or EDTA is recommended as anticoagulant for whole blood or bone marrow collection
- Sodium heparin and sodium citrate are compatible with the immunoSEQ Assay. However, excessive amounts of sodium heparin can inhibit PCR
- Roughly 50% of cells frozen in DMSO will lyse during the thawing process. To recover all DNA do not centrifuge the sample after thawing. Instead, extract DNA from the entire thawed sample
- Possible extraction kits:
 - Qiagen DNeasy™ Blood & Tissue Kit (Mini Spin Columns): Bone marrow and <1 mL blood
 - Qiagen QIAamp™ DNA Blood Maxi Kit: 1–10 mL blood

Shipping Samples

- Cells and tissue: 1.5 or 2.0 mL Eppendorf tubes/ cryotubes (snap top or screw cap)
- Whole blood: Vacutainer ACD or EDTA tube, completely filled
- gDNA or cDNA: Uniquely barcoded sample containers will be provided by Adaptive Biotechnologies.

Quality of input DNA

Once DNA is isolated, quantification using a spectrophotometer or comparable method is highly recommended. For optimal results the absorbance ratios of DNA samples should be:

- $A_{260}/280 = 1.8\text{--}2.0$
- $A_{260}/230 = 2.0\text{--}2.2$

Potential PCR inhibitors

Sample source(s) containing any of the following may inhibit PCR steps used in the immunoSEQ Assay:

- **Heparin, EDTA**, common anticoagulants in blood and bone marrow samples
- **Melanin**, common to skin and melanoma tissue samples
- **B5 Reagent**, commonly used for bone marrow storage
- **Collagen**, can be at high levels in some tissue samples
- **Myoglobin**, common to muscle tissue
- **Bacterial contamination** from all sample sources
- **Phenol, ethanol, and other organic contaminants** remaining after DNA extraction

For questions or Technical Support contact:
[contact], or [contact]

